4.3.5 Pharmacokinetic analysis

The PK and exposure-response correlation study will be performed in 24 participants in the two treatment arms receiving either ivermectin ODT 200 μ g/kg or ivermectin standard tablets 200 μ g/kg (12 per selected treatment arm). Since PK population parameters of ivermectin are available, a sparse sampling approach can be applied to describe the PK profile [31]. Within a sparse sampling approach, instead of describing the PK profile for each participant separately, samples are allocated to different time points and/or individuals within the same treatment. Statistical inferences are performed to characterize the population-based PK profile of a specific treatment arm. This approach allows for a reduced number of samplings per treatment arm and renders a PK characterization well tolerable. To this end, a small drop of blood from the fingertip will be taken for a maximum of 5 finger pricks per participant. The exact time points are 1h, 2h, 4h, 6h, and 24h, covering the relevant time span identified previously [31, 32]. Capillary blood (~60 μ l) will be collected by puncture with a finger prick. Two micro-samples (duplicates) will be taken with one finger prick. Each time, the drop of blood (60 μ l) will be directly transferred on dried-blood spot cards. The dried cards will be transported to Swiss TPH and stored at room temperature until analysis (< 2 months post-treatment). The quantification of the study

drugs will be performed using the validated liquid chromatography tandem mass spectrometry (LC-MS/MS) method as described elsewhere [32]. Drug concentrations will be calculated by interpolation from a calibration curve with a lower limit of quantification of 1-5 ng/ml. 7% of the sample duplicates will be analysed for quality control, and the measured concentrations will be used to determine between-run and overall precision and accuracy of the analysis.

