7.2 Data collection and documentation

Data collected and produced within this trial will fall into one of the following categories:

- a) Egg counts of *T. trichiura*, *A. lumbricoides* and hookworm derived from quadruplicate Kato-Katz microscopy performed at baseline as well as at 14-21 days post-treatment.
- b) Anthropometric and clinical characteristics of the trial participants collected using the study's CRF such as weight, height, blood pressure, temperature, overall health status and any abnormal medical condition or chronic disease.
- c) Finger prick blood samples for haemoglobin measurement and PK analysis.
- d) Collection date and time of each PK sample.
- e) Measured concentrations analysed from finger prick blood samples and subsequently derived PK parameters.

All data categories will be recorded paper-based (primary data source), *e.g.* on the CRF, and double-entered into the electronic data collection software REDCap (Vanderbilt University, US) using tablets. In this case, the paper-based data will represent the primary data source. All entries will be printed in blue ink and all corrections must be documented with date and initials of the respective team member. Double-entered data will be compared using the REDCap internal 'Data Comparison Tool' and any discrepancies will be reviewed against the hardcopies of the CRF and corrected accordingly. All data files in REDCap will be merged into a master file and saved as .xlsx and/or .csv file. Data analysis will be conducted with pseudonymised data and reporting of findings will be fully anonymised.

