8.3 Description of statistical methods

The primary analysis will use the full analysis set (available case population) according to the intention-to-treat principles defined as all randomised participants who provide any follow-up data. Only randomised participants not providing follow-up data as well as participants who were negative at baseline and erroneously randomised will be excluded from the analysis. In addition, a per-protocol analysis will be conducted. Eligibility for analysis sets will be determined before unblinding. CRs will be calculated as the percentage of egg-positive participants at baseline who become egg-negative after treatment.

EPG will be assessed by adding up the egg counts from the quadruplicate Kato-Katz thick smears and multiplying this number by a factor of six. Geometric and arithmetic mean egg counts will be calculated for the different treatment arms before and after treatment to assess the corresponding ERRs (see formula).

$$ERR = 1 - \frac{\frac{1}{n} e^{\sum \log(EPG_{follow-up} + 1)} - 1}{\frac{1}{n} e^{\sum \log(EPG_{baseline} + 1)} - 1}$$

Bootstrap resampling method with 5,000 replicates will be used to calculate 95% confidence intervals (CIs) for ERR point estimates. Using the DoseFinding package of the statistical software environment R, hyperbolic E_{max} models will be implemented to predict the curves of the dose-response in terms of CRs and ERRs.

Previous similar trials have shown that the proportion of participants lost to follow-up is usually far below 10%, therefore, no imputation of missing data will be performed. Infection status and egg counts of participants with incomplete data at follow-up (*i.e.* only one stool sample available at follow-up) will be estimated based on the available data. This means a participant is considered infected if any sample is positive and EPGs will be calculated as mean egg count of the available sample multiplied by 12.

The safety analysis set will include all treated participants. AEs will be evaluated descriptively focusing on the proportion of participants reporting symptoms before and after treatment in each arm.

Previously established nonlinear mixed-effects (NLME) models will be used to compare and determine PK parameters [21]. Concentrations are measured with a validated LC-MS/MS method [32]. Using NLME, the following key PK parameters will be calculated:

- C_{max} maximal plasma concentration
- t_{max} time to reach C_{max}

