- AUC area under the curve, from 0 to 24 h and 0 to inf.
- $t_{1/2}$ elimination half-life

 C_{max} and t_{max} will be observed values derived from the plasma concentration-time profile. Total drug exposure (AUC) and $t_{1/2}$ will be calculated with the WinNonlin software package using compartmental analysis. The elimination half-life will be estimated by the equation: $t_{1/2} = \ln 2/\lambda$, where λ (the elimination rate constant) will be determined by performing a regression of the natural logarithm of the concentration values during the elimination period. Primary PK parameters including absorption rate (k_a), volume of distribution (V), and clearance (CL) will be estimated utilizing NLME modelling. In addition, exploratory pharmacometric PK and exposure-response analyses may be performed with the Monolix or NONMEM software package.

The VAS score for the palatability will be summarised using descriptive statistics according to formulation (ivermectin ODT, and ivermectin standard tablets crushed and swallowed with water). Each of the arms receiving the new formulation (arm A, B, C, D and E) will be tested against the current formulation (Arm F).

9. Duties of the investigator

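### Section 8.3 defines Cmax and its source profile as plasma, but only dried capillary whole blood is assayed and no conversion is planned

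*Combined protocol and SAP*

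**What the plan says.** On sampling, section 4.3.5 says that about 60 µl of capillary blood "will be collected by puncture with a finger prick" at 1, 2, 4, 6 and 24 hours, and that each drop "will be directly transferred on dried-blood spot cards". The cards are then assayed by LC-MS/MS using the method in reference 32, whose title describes a dried-blood-spot method. Section 7.2 lists the resulting data as "Measured concentrations analysed from finger prick blood samples and subsequently derived PK parameters". The synopsis also speaks of blood micro-samples.

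On analysis, section 8.3 defines Cmax as "maximal plasma concentration" and states that Cmax and tmax "will be observed values derived from the plasma concentration-time profile". AUC is described only as "area under the curve, from 0 to 24 h and 0 to inf"; total exposure and half-life "will be calculated with the WinNonlin software package using compartmental analysis". No matrix is named for AUC, clearance or volume. Earlier NLME models (reference 21) are to be used to compare and determine PK parameters, again with no matrix named.

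**The concern.** The plan measures one matrix and names another in the definition of a reported parameter. No venous draw, plasma separation, blood-to-plasma ratio or haematocrit adjustment appears anywhere in the document, so the plasma profile from which Cmax and tmax are to be read will not exist.

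Population PK is secondary objective (d), and section 2 says that the PK data will help guide dosing in this age group. Someone who reads a plasma Cmax in the report may set it beside plasma values from other studies. Whether that is valid depends on how ivermectin distributes between red cells and plasma, which the documents do not address. The absolute values at stake are Cmax and, if the label carries over, AUC, clearance and volume.

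**Working it through.** The plan states no figure to reproduce here. The check is a comparison of text, followed by an illustration of size under stated assumptions.

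**Step 1: matrix sampled against matrix named**

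| Item | Matrix | Place |
|---|---|---|
| Sample collected | Capillary blood, dried on cards | 4.3.5 |
| Assay | Dried blood spots | Title of reference 32 |
| Recorded concentrations | Finger-prick blood | 7.2 |
| Cmax | Plasma | 8.3 |
| Profile giving Cmax and tmax | Plasma | 8.3 |
| AUC, CL, V | Not stated | 8.3 |
| Model in reference 21 | Not stated | 8.3 |

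Plasma is therefore explicit for Cmax and for the profile. For AUC it is only implied, because the plasma profile is the only concentration-time curve that section 8.3 names. The PK sample is 12 × 2 = 24 children with at most 24 × 5 = 120 sampling points, all from finger pricks.

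**Step 2: size of the discrepancy**

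Formula: blood/plasma ratio R = (1 − H) + H × K, where H is haematocrit and K is the red-cell-to-plasma concentration ratio.

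Inputs:
- Hb 70 g/l is the severe-anaemia threshold in exclusion criterion 1 (section 5.3).
- Hb 130 g/l as an upper value is an assumption.
- H = 3 × Hb (g/dl)/100 is an assumption. It gives 3 × 7/100 = 0.21 and 3 × 13/100 = 0.39.
- K is not in the documents, so a range is shown.

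| K (assumed) | R at H = 0.21 | R at H = 0.39 |
|---|---|---|
| 0 (no red-cell uptake) | 0.79 | 0.61 |
| 0.5 | 0.79 + 0.105 = 0.895 | 0.61 + 0.195 = 0.805 |
| 1 (equal partition) | 1.00 | 1.00 |
| 1.5 | 0.79 + 0.315 = 1.105 | 0.61 + 0.585 = 1.195 |

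At K = 0, a whole-blood value labelled as plasma is 21% to 39% too low. At K = 1 there is no error. Above K = 1 it is too high.

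**Step 3: which parameters are affected**

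If R is constant, every concentration is multiplied by R. Cmax and AUC then scale by R, and apparent CL and V by 1/R. As a check, a one-compartment profile with arbitrary rate constants (absorption 0.4 per hour, elimination 0.03 per hour) was read at the five protocol times, with AUC by the trapezoidal rule from 1 to 24 hours:

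| R | Cmax | AUC | tmax | Slope 6–24 h |
|---|---|---|---|---|
| 1.0 | 0.805 | 15.226 | 6 h | 0.0236 |
| 0.8 | 0.644 | 12.181 | 6 h | 0.0236 |
| 0.6 | 0.483 | 9.136 | 6 h | 0.0236 |

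Cmax and AUC fall by 20% and 40%, while tmax and the terminal slope do not move. In the formulation comparison both arms use the same matrix, so (R × ODT)/(R × tablet) = ODT/tablet and R cancels.

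**The case against.** The strongest reply is that this is loose terminology. Sections 4.3.5 and 7.2 and the title of reference 32 leave no doubt about what is measured, and the PK objective is ODT against standard tablet, both at 200 µg/kg and both in the same matrix. A constant ratio drops out of that contrast. This stands, and it confines the problem to absolute values. It does not remove it: section 8.3 is the operative definition, and it uses *plasma* both where Cmax is defined and where it is derived.

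A second reply is that the NLME model in reference 21 may contain a conversion, or may itself rest on blood data. The documents do not show either. If it rests on blood data, comparison with it is like with like and only the label is wrong. A conversion inside the model would not reach Cmax and tmax, because section 8.3 and the synopsis both say these are observed values (although section 8.3 also lists them among the NLME parameters).

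A reader might go further and infer that children will look under-exposed relative to adults because of the matrix. The documents do not support that. Section 2 mentions equivalent bioavailability as background from an earlier study. No child-versus-adult comparison of absolute concentrations is prespecified, no earlier PK source is shown to be plasma-based, and the direction of any bias depends on K.

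**Conclusion.** The contradiction is certain from the text: whole-blood Cmax would be reported as plasma Cmax, and AUC, CL and V would be read the same way by implication. It should be corrected, because it sits in the definition of parameters serving a stated secondary objective.

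The numerical consequence is not known. The range of R (0.79 to 0.61 with no red-cell uptake, 1.0 with equal partition, above 1 with red-cell concentration) rests on an assumed partition ratio, an assumed upper Hb and an assumed Hb-to-haematocrit factor. It is a range of possibilities and not an estimate of bias. It would also be too strong to say that section 8.3 explicitly defines exposure in plasma, since AUC has no stated matrix.

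That tmax, half-life and the ODT-versus-tablet ratio are unaffected holds under a constant ratio. The primary endpoint and the dose-response analysis do not use these data.

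**What to change.** In section 8.3:

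1. Replace *plasma* with *dried capillary whole-blood (dried blood spot)* in the definition of Cmax and in the description of the concentration-time profile.
2. State the same matrix for AUC, CL and V.
3. State the matrix of the previously established NLME model in reference 21.
4. Add that absolute values will be compared only with data from the same matrix. If a comparison with plasma data is wanted, state the conversion (ratio, its source and how haematocrit is handled) and a sensitivity range for the ratio.

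A haematocrit-based conversion is not needed to resolve the contradiction, and without a sourced ratio it would put assumed values into measured data. Baseline Hb, already measured in every child, can be examined as a covariate, but with 24 PK children this should be labelled exploratory.

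The cost is a wording change in one section. No new samples, visits or assays are needed.

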4.2 Trial design

A parallel randomised controlled dose-ranging trial will be conducted with six treatment arms (Figure 1). The study includes a baseline screening (day -60 to -1) and clinical baseline assessment (day 0) before treatment and post-treatment assessments for, pharmacokinetics (day 0 to 1), safety (day 0, 1 and 14 to 21) and efficacy (day 14 to 21). It is designed as a dose-ranging trial with 210 participants aged 2-5 years randomised to ivermectin ODT placebo and albendazole (400 mg), ascending doses of ivermectin ODT ($100 \mu g/kg$, $200 \mu g/kg$, $300 \mu g/kg$, or $400 \mu g/kg$, respectively) and albendazole (400

mg), or the standard ivermectin tablets (200 μg/kg) and albendazole (400 mg), with an allocation ratio of 1:1:1:1:1:1 (*i.e.*, 35:35:35:35:35:35:35). This trial will be conducted in communities in the Wete district on Pemba Island with high endemicity as identified in previous studies on *T. trichiura*.

[figure not shown]

Figure 1. Trial design and timeline.

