4.3.4 Treatment of participants

All eligible participants will be treated with the respective treatment regimen according to their treatment arm assigned by randomisation at day 0. Ivermectin tablets (ODT and standard tablets) will be obtained from Liconsa, and an individual number of tablets according to bodyweight and dose will be administered. Albendazole will be the product of GSK (Zentel®) and a single tablet of 400 mg will be administered. Placebo tablets will be purchased from Zentiva Pharma GmbH, Germany.

The tablets will be handed out from four drug containers (placebo, ivermectin ODT, ivermectin standard tablets, and albendazole). According to the randomisation list, each person will receive either:

- (i) Placebo (number corresponding to 200 µg per kg bodyweight) plus a single tablet of albendazole
- (ii) 100 μg ivermectin ODT per kg bodyweight plus a single tablet of albendazole
- (iii) 200 µg ivermectin ODT per kg bodyweight plus a single tablet of albendazole

- (iv) 300 µg ivermectin ODT per kg bodyweight plus a single tablet of albendazole
- (v) 400 µg ivermectin ODT per kg bodyweight plus a single tablet of albendazole
- (vi) 200 µg ivermectin standard tablets per kg bodyweight plus a single tablet of albendazole

All drugs will be administered in the presence of the Principal Investigator (PI) and/or Co-PI, and ingestion confirmed. This will be recorded with the time and date of dosing. Participants will be asked to limit the use of any drugs other than those prescribed by the study medical team for the duration of the study as described in section 5.5. After ingestion of the medication, the participants will be observed for three hours to ensure retention of the drug. Vomiting within one hour post-dosing will require redosing. The participants will not be allowed more than one repeated dose. No re-administration will be needed for participants vomiting after one hour. The PI or the Co-PIs are responsible for drug accountability at the study site. Maintaining drug accountability includes careful and systematic study drug storage, handling, dispensing, and documentation of administration. Prior to administration, drugs will be stored at room temperature and protected from light and exposure to moisture in a secure area with limited access at the study site.

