4.3.6 Assessment of acceptability

To better understand the acceptability of ivermectin ODT compared to standard ivermectin tablets in PSAC, the palatability of each formulation (ODT and standard tablets crushed and swallowed with water) will be rated by children aged 4-5 years using a 100 mm VAS incorporating a 5-point pictorial hedonic scale (Figure 2) [33]. This rating will take place within 5 minutes after receiving the treatment. Additionally, participants will complete a short questionnaire directly after treatment administration and the interviewers will observe the participants during medication administration and record any discomfort or difficulties in taking the medication.

[figure not shown]

Figure 2. 100 mm hedonic visual analogue scale [33].

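### The palatability analysis does not name ODT 200 µg/kg versus standard tablet 200 µg/kg as the formulation comparison, so its pooled summary and most of its tests mix formulation with dose

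*Combined protocol and SAP*

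**What the plan says.** All references are to the combined protocol and SAP.

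- **Doses.** Section 4.2 describes "ascending doses of ivermectin ODT" at 100, 200, 300 and 400 µg/kg. Section 4.3.4 gives the standard tablet at 200 µg/kg only.
- **Amount taken.** Section 4.3.4: "an individual number of tablets according to bodyweight and dose will be administered". It also says: "The tablets will be handed out from four drug containers (placebo, ivermectin ODT, ivermectin standard tablets, and albendazole". There is one ODT container, and the strength per unit is not given for either formulation.
- **Placebo.** In section 4.3.4 the number of placebo tablets is matched to 200 µg/kg. They come from a different supplier than the ivermectin products.
- **Rating.** Section 4.3.6 sets out to compare the ODT with the standard tablet. Palatability "will be rated by children aged 4-5 years using a 100 mm VAS", once, within 5 minutes of treatment. The items in Appendix 15.1 cover presence of taste, bitterness, sweetness and liking.
- **Analysis.** Section 8.3: "The VAS score for the palatability will be summarised using descriptive statistics according to formulation". The next sentence reads: "Each of the arms receiving the new formulation (arm A, B, C, D and E) will be tested against the current formulation (Arm F". No test, significance level or order of priority is given, and nothing is split by dose or by number of units.

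**The concern.** Acceptability is a secondary objective, and section 4.3.6 asks how the ODT compares with the standard tablet. For that question the two groups should differ in formulation and not in dose. Only one of the planned contrasts meets this at the level of µg/kg, and it has no special standing.

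If taste scores depend on the amount of drug in the mouth, the pooled ODT summary carries a dose component. So do the tests of the 100, 300 and 400 µg/kg arms against the tablet, in different directions. A report could then credit or blame the formulation for a difference that comes from dose.

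A second matter concerns who is compared. There are six arms, and F is the standard tablet. Whatever the order of the letters, the other five must include placebo, yet section 8.3 describes all five as receiving the new formulation.

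**Working it through.** **Inputs from the documents.** Six arms of 35 (6 × 35 = 210, the stated total); ODT at 100, 200, 300 and 400 µg/kg; tablet at 200 µg/kg; raters aged 4-5 years only. The plan states no figure for palatability, so there is none to reproduce beyond the arm size.

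**Assumptions.** 40-60% of each arm is aged 4-5, giving 35 × 0.4 = 14 to 35 × 0.6 = 21 raters per arm (17.5 at 50%). The VAS standard deviation is 25-35 mm. The effect of dose on the score is unknown and is varied below.

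**1. Dose relative to the tablet arm**
- By arm: 100/200 = 0.5; 200/200 = 1.0; 300/200 = 1.5; 400/200 = 2.0.
- Four ivermectin ODT arms pooled: (100 + 200 + 300 + 400)/4 = 250 µg/kg, or 1.25 times the tablet arm.
- With placebo counted at its matched number: (200 + 100 + 200 + 300 + 400)/5 = 240, or 1.2 times.

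**2. Dose is not the same as tablet count**
- The dose ratio from lowest to highest ODT arm is 400/100 = 4.
- The count ratio depends on unit strength and rounding. For assumed strengths of 0.25-3 mg and weights of 12-20 kg, whole-tablet counts give ratios from 2 to 6. Example: a 14 kg child with 1 mg units needs 1.4 mg (1 unit) or 5.6 mg (6 units), rounding to nearest.

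**3. Possible shift if the score is linear in dose, b mm per 100 µg/kg**
- By arm against tablet: -b (100), 0 (200), +b (300), +2b (400).
- Pooled: (-b + 0 + b + 2b)/4 = 0.5b.
- With b = 5 (assumed; range 2-10): 2.5 mm (1-5) pooled and 10 mm (4-20) for the 400 µg/kg arm.

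**4. Possible shift if the score moves 10 mm per doubling of dose (assumed)**
- By arm: -10, 0, +5.85 and +10 mm.
- Pooled: 5.85/4 = 1.46 mm. Low and high doses largely offset.

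**5. Precision, at 17.5 raters per arm**
- ODT 200 versus tablet 200: √(2/17.5) = 0.338 SD.
- Four ODT arms pooled versus tablet: √(1/70 + 1/17.5) = 0.267 SD.
- Formulation effect at 200 µg/kg from a model with a linear ODT dose slope: √(1/70 + 50²/(70 × 12500) + 1/17.5) = 0.273 SD. Here 12500 is the variance of the four doses. The gain over the direct pair is 1 - 0.273/0.338 = 19%, whatever the number per arm.

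**6. Detectable difference (80% power, two-sided 5%)**
- Formula for the dose-matched pair: (1.960 + 0.842) × SD × √(2/n).
- Dose-matched pair: 21.6 mm (n = 21, SD 25) to 37.1 mm (n = 14, SD 35).
- Pooled, with √(1/n + 1/(4n)): 17.1 to 29.3 mm.

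**7. Can the linear model stand in for the direct pair?**
- Fit it to the shifts in step 4, with doses centred at -1.5, -0.5, 0.5 and 1.5 (units of 100 µg/kg).
- Slope = (15 + 0 + 2.925 + 15)/5 = 6.585 mm per 100 µg/kg.
- Fitted value at 200 µg/kg = 1.46 - 0.5 × 6.585 = -1.83 mm, where the true value is 0.
- That error is larger than the pooled shift of 1.46 mm. The 19% gain is therefore available only if the effect really is linear.

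**The case against.** The strongest reply is that section 8.3 already tests each ODT arm against F, so the dose-matched pair is in the plan. That is right. A reader might infer that the trial has no like-for-like comparison, and the documents do not support it. What remains is that this pair is one of five tests of equal standing, beside a summary that pools over dose.

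The formal objective is the acceptability of the treatments, and dose is part of a treatment. On that reading each arm-wise test is legitimate. This also stands, but such tests then compare treatments, while section 4.3.6 asks about formulations.

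The VAS items concern taste, not the number of tablets, and difficulty in taking the medicine is recorded separately. The documents give no evidence that taste scores change with amount. They give none that they do not, and one rating follows the whole dose.

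A reader might also infer that the ODT result is known to be materially biased, or that children in the top arm take four times as many tablets as those in the lowest. Neither is established. The slope is assumed, and the pooled shift in steps 3 and 4 is small beside the detectable difference. Unit strengths are not stated, so fourfold describes dose and not count. For the same reason, equal µg/kg need not mean equal units even at 200 µg/kg.

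On placebo, section 4.2 calls it an ODT placebo and section 4.4 says it matches in appearance and texture. Neither claims a match in taste, and it contains no ivermectin.

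**Conclusion.** The point holds as a matter of labelling and priority in the analysis. The by-formulation summary compares a mean of 250 µg/kg with 200 µg/kg, and the tests of the 100, 300 and 400 µg/kg arms compare 0.5, 1.5 and 2 times the tablet dose with it. All of these mix formulation with dose. The one contrast that does not is planned but not identified as the answer to the formulation question. Describing all of arms A-E as receiving the new formulation is wrong for the placebo arm. The arm letters are not defined in the text and Figure 1 is not shown, but this conclusion needs only that F is the standard tablet and that there are six arms.

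The shift cannot be determined from the documents. Under the assumed slopes it is about 1-5 mm in the pool, where doses partly offset, and 4-20 mm for the 400 µg/kg arm. This is a secondary, largely descriptive endpoint and the primary analysis is untouched. The change is worth making because it costs no data.

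**What to change.** In section 8.3:

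1. Define arms A-F in the text.
2. Name ODT 200 µg/kg versus standard tablet 200 µg/kg as the main palatability contrast for formulation, and report the difference with a 95% confidence interval.
3. Tabulate VAS scores by dose arm and by number of units taken, instead of only pooled by formulation.
4. Keep the placebo arm out of any ODT pool and out of any test described as concerning the new formulation.
5. Present the other ODT arms versus F as comparisons of treatments, not of formulation.
6. Optionally add a model with formulation plus a linear ODT dose slope as a sensitivity analysis. It should not replace the direct contrast (step 7 of the working).

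The cost is analysis wording, with no new data beyond the tablet numbers already set at dosing. The price is precision. The main contrast rests on two arms, about 14-21 raters each under the 40-60% age assumption, with a standard error of 0.338 SD against 0.267 SD for the pooled comparison. No change to any dose is implied.
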